8.2 Subject Accountability

All subjects enrolled (with ICF signed) for the study will be used for reporting of disposition. Subject disposition summaries will include the number and percentage of subjects who consist of each analysis population, such as the FAS, safety, etc. The number and percentage of subjects who received study drug treatment, completed the study or discontinued the study (with reasons) will be summarized.

8.3 Protocol Deviations

Protocol deviations, both major and minor, will be listed. Major protocol deviations will also be summarized.

8.4 Investigational Product Administration

8.4.1 UX007 Dosing, Exposure, and Diet

UX007 dosing and exposure parameters will be summarized based on UX007 treatment regimen log. Descriptive summary statistics will be produced for the following parameters.

- Total duration of UX007 exposure
- Overall average prescribed UX007 dose
- % of daily caloric intake provided by prescribed UX007 dose
- Total daily prescribed dose in mg/kg/day

In addition, % of daily caloric intake provided by daily UX007 intake will be derived using the 3-day average based on the 3-day diet diary. Daily caloric intake (total calories per kg), daily protein intake (% of total caloric intake), daily carbohydrate intake (% of total caloric intake), daily total fat intake (% of total caloric intake), and daily UX007 intake (% of total caloric intake) will be summarized by visit using descriptive statistics.

Profile figures for individual subjects will be generated to display dietary parameters along with the occurrence of MCEs on the same plot, over the combined pre- and post- UX007 treatment period. Prescribed %DCI of the macronutrient intakes (UX007, MCT, other fat, carbohydrates, and protein) and total caloric intake (TCI) will be displayed over time

Data listings will be generated displaying the 3-day average subject diet diary parameters which includes fat, carbohydrates, and protein measured in g/kg/day and %DCI will be provided for the CL201-Rollover and the Naïve Cohort separately.

8.4.2 Treatment Compliance

Summary statistics will be produced for the following UX007 treatment compliance parameters based on dosing compliance diary.

- Overall UX007 dosing completion percentage as defined in Section 5.17.
- Number and percentage of subjects with overall UX007 dosing completion percentage $\geq 80\%$

8.4.3 Demographic and Baseline Characteristics

Summary statistics will be presented for the Full Analysis Set and by subgroup for the following (but not restricted) parameters

- Gender

- Ethnicity
- Race
- Gestational age at birth
- Age at enrollment (ICF date)
- Age at LC-FAOD diagnosis
- Age at first dose of UX007 (in CL202)
- Age at first dose of UX007 (only for CL201 rollover subjects and UX007/trihep naïve subjects)
- Height at baseline
- Weight at baseline
- BMI at baseline

As only limited demographics data (i.e., date of birth and sex) and LC-FAOD diagnosis and LC-FAOD medical history are entered into the clinical database for subjects who previously participated in the UX007-CL001 or UX007-CL201 study, the UX007-CL001 and UX007-CL201 databases will be integrated with UX007-CL202 database to obtain complete data on demographics , LC-FAOD diagnosis, and LC-FAOD medical history.

8.4.4 Prior and Concomitant Medication

Prior medication is defined as any medication started before the date of the first dose of UX007 in CL202.

Concomitant medication is defined as any medication taken during the study that starts on or after the date of the first dose of UX007 in CL202. A medication started before the date of the first dose of UX007 and also taken after the date of first dose of UX007 during CL202 will be counted both as a prior and concomitant medication.

Concomitant medications will be coded using the latest World Health Organization (WHO) Drug Dictionary.

If a subject took a specific medication multiple times or took multiple medications within a specific therapeutic class, that subject will be counted only once (i.e., subject incidence) for the coded drug name or therapeutic class.

8.5 Efficacy Analysis

An overview of efficacy analyses is provided below.

The efficacy analyses will be based on FAS unless otherwise specified. The analysis of SF-10 and SF-12V2 will be based on the FAS-SF-10 and FAS-SF-12, respectively. Safety analyses will be based on the safety analysis set. All analyses will be presented by subject cohort unless otherwise specified.

The primary efficacy analysis of the annualized MCE rate will be summarized using descriptive statistics with mean, standard deviation (SD), median, quartiles, minimum, and maximum values.

Secondary efficacy analysis on cardiac function endpoints based on ECHO and annualized event/duration rates for MCE by event type will be performed in a similar fashion as with the primary efficacy endpoint.

Summary statistics will be produced for all exploratory endpoints using all available assessments. For continuous variables, the number of observations and the mean, standard deviation (SD), median, quartiles, minimum, and maximum values will be tabulated. For categorical variables, the counts and percentages of will be tabulated. Two-sided 95% confidence interval will also be provided.

For UX007/trihep naïve subjects, efficacy will be assessed by comparing pre- and post-UX007 MCE rates for MCE related endpoints and by testing change from baseline for non-MCE efficacy endpoints; See section 8.5.4 for details.

For UX007-CL201 rollover subjects, an integrated analysis by combining data collected from UX007-CL201 and UX007-CL202 to assess the long-term effects of UX007 on key efficacy parameters; See section 8.5.5 for details.

8.5.1 Analysis of Primary Efficacy Endpoint

The primary efficacy parameter is the annualized MCE event rate inclusive of skeletal myopathy (rhabdomyolysis), hepatic (hypoglycemia) and cardiomyopathy events. Study period 1, or the main study period, will be used for the primary efficacy analysis. Annualized MCE event rate will be calculated for the entire study period 1 and by 18-month interval. The descriptive statistics will be provided using the methodology specified in Section 8.1.

The numbers of MCE events will also be summarized by precipitating factors (infectious disease, exercise, other, and unknown) and by type of intervention (emergency intervention, hospitalization, and ER visit).

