This open-label long-term safety and efficacy study will provide an opportunity for LC-FAOD patients to be treated with UX007 for up to 7 years or until commercial availability of UX007 in any region, whichever occurs first, under a single standardized protocol. The subjects may have participated in other studies or treatment programs with UX007/triheptanoin or be treatment naïve and have clear unmet need but would be consolidated into one program for long-term triheptanoin treatment and consistent safety monitoring. The study is designed to obtain long-term safety information and evaluate maintenance of efficacy in a diverse LC-FAOD population.

OBJECTIVES:

The primary objective of the study is to:

• Evaluate the long-term safety and efficacy of UX007 in LC-FAOD subjects

The secondary objectives of the study are to:

- Evaluate the effect of UX007 on energy metabolism in LC-FAOD
- Evaluate impact of UX007 on clinical events associated with LC-FAOD

The objective of the pharmacokinetic sub-study is to:

• Characterize the steady-state pharmacokinetics (PK) of UX007 and UX007 metabolites in subjects with LC-FAOD

ENDPOINTS:

Efficacy Endpoints

The primary efficacy endpoint:

• The annualized LC-FAOD major events rate inclusive of skeletal myopathy (rhabdomyolysis), hepatic (hypoglycemia) and cardiomyopathy events.

The secondary efficacy endpoints:

- Energy metabolism in LC-FAOD on the basis of the following endpoints:
 - Ventricle size
 - Ejection fraction (EF)
 - Shortening fraction (SF)
- Clinical events associated with LC-FAOD on the basis of the following endpoints
 - Annualized duration rate of all MCEs
 - Annualized event rate of rhabdomyolysis MCEs
 - Annualized duration rate of rhabdomyolysis MCEs
 - Annualized event rate of cardiomyopathy MCEs
 - o Annualized duration rate of cardiomyopathy MCEs
 - Annualized event rate of hypoglycemic MCEs
 - Annualized duration rate of hypoglycemic MCEs

Exploratory endpoints include the following:

- Functional disability and cognitive development (instrument selection based on age) endpoints:
 - SF-10 physical health component summary (PCS) score
 - SF-10 mental health component summary (MCS) score
 - o SF-12 physical health component summary (PCS) score
 - SF-12 mental health component summary (MCS) score
- Clinical biomarkers endpoints:
 - Serum creatine kinase
 - Fasting serum glucose
 - Alanine aminotransferase (ALT)
 - Aspartate transaminase (AST)
 - Gamma glutamyl transpeptidase (GGT)

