7.3.3.1 Stopping Rules

Individual subjects who experience a Grade 3 or higher SAE that is unexpected and possibly, probably, or definitely related to UX007 (Section 8.5.3) that represents a change in the nature or an increase in frequency of the serious event from their prior medical history will be assessed, by the Investigator, as to whether the subject will continue on the study.

Commonly occurring LC-FAOD medical events include rhabdomyolysis, cardiomyopathy, hypoglycemia, and other events as described in the IB. If a subject experiences a major LC-FAOD medical event, which represents a change in the nature or an increase in frequency of the serious event from their prior medical history, the Investigator should determine whether the subject should be discontinued from the study. In these cases, the

subject visit schedule may need to be modified or assessments withheld to allow the subject to continue as deemed appropriate by the Investigator.

Regulatory Authorities, as well as the IRBs/ECs, will be informed should unexpected and possibly, probably, or definitely drug-related SAEs occur, a full evaluation of the event will be performed in order to make a decision regarding what actions to take, including whether to recommend stopping the study. Regulatory Authorities, as well as IRBs/ECs, will be informed if the study is paused or stopped. If the Sponsor deems it appropriate to restart the trial following an internal safety review, this will be done only following approval by Regulatory Authorities.

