7.5.2.3 LC-FAOD Major Events

Major LC-FAOD events include skeletal myopathy (rhabdomyolysis), hepatic (hypoglycemia) and cardiac disease (cardiomyopathy) events, and are defined as any visit to the ER/acute care, hospitalization, emergency intervention (i.e. any unscheduled administration of therapeutics at home or in the clinic), or any similar event whether caused primarily by LC-FAOD or by an intercurrent illness complicated by LC-FAOD. The event type, levels of relevant laboratory parameters (including CK, glucose, and BNP/troponin), the number of days hospitalized and in ICU, and the type and number of days of treatment and intervention will be recorded.

By definition, events requiring inpatient hospitalization or that cause persistent or significant incapacity or substantial disruption of the ability to conduct normal life functions, are classified as a serious adverse event (SAE) or serious suspected adverse reaction, and will be reported as described in Section 8.5. If the event represents a substantive change in the nature or an increase in frequency from a subject's prior medical history, the event should be reported as an adverse event (AE) and the Investigator should evaluate whether the subject should be discontinued from the study.

In these cases, the subject visit schedules may need to be modified or assessments withheld to allow the subject to continue as deemed appropriate by the Investigator. Information on the incidence of major rhabdomyolysis events will be collected at each visit.

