5.11 Annualized Event Rate

The numbers of MCE will be annualized for each subject using the following formula:

$$\text{Annualized Event Rate} = \frac{\text{Number of events}}{\text{Duration of data collection period in days}/365.25}$$

The number of MCEs will be derived as the total number of events as recorded in the major clinical event CRF that occurred during the specific data collection period. Whenever an annualized rate is calculated over study period 1, the number of days is calculated from study day 1 till the data cutoff date or the early termination/study completion visit date for subjects who have early terminated/completed the study.

Annualized event rates will be calculated for MCEs overall and for each event type (ie., rhabdomyolysis, hypoglycemia, and cardiomyopathy respectively).

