6 ANALYSIS POPULATIONS

6.1 Full Analysis Set (FAS)

The full analysis set (FAS) will consist of all subjects enrolled and had at least one post-baseline efficacy assessment. The full analysis set will be used for efficacy analyses.

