8.5.5.1 Pre- and Post-UX007 MCEs in CL201-Rollover Cohort

Annualized event and duration rates of MCE and by MCE type will be calculated for the three time periods: study period 3 (i.e., 18 months pre-UX007 treatment period), the 18 month CL201 treatment period, and study period 1 (CL202 UX007 treatment period). Within study period 1, annualized event/duration rates will be calculated by 18-month time interval. Summary statistics will be provided for calculated annualized event/duration rates. In addition, annualized event/duration rates will be plotted as box plots over time to show the time trend.

Annualized event rates (AER) and Annualized Event Duration rates (AED) will be analyzed by comparing pre- and post-UX007 treatment period. The pre-UX007 treatment period for UX007-CL201 Rollover subjects corresponds to study period 3.

For subjects who had longer than 18 months of follow up on study (CL202) as of the data cutoff date, MCEs that occurred between UX007 initiation and 18 months post UX007 initiation will be included for calculating number of MCEs and total durations in days of MCEs will be calculated accordingly. For subjects who terminated the study prior to reaching 18 months on study, MCEs that occurred between UX007 initiation and the termination visit will be included for calculating number of MCEs and total durations in days of MCEs will be calculated accordingly. For historical annualized event rate and annualized duration rate observed during study period 3, the data collection period is 18 months (548 days) preceding the date of UX007 initiation. For subject's age less than 18 months at UX007 initiation, the data collection period will be between the birthdate and the date prior to UX007 initiation.

Patient level plots to show all MCEs over time and time-points of start of retrospective period relative to the UX007 initiation and early discontinuation in a subject if applicable will be presented.

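### MCE rates by 18-month interval rest on whoever is then under observation, so if leaving is related to MCEs the interval means can fall with no change in any subject's true rate

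*SAP*

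**What the plan says.** The protocol synopsis gives as one design aim to "evaluate maintenance of efficacy in a diverse LC-FAOD population". Protocol 7.6.6 and SAP 3.6 also mention indicators of durability when describing the sample size.

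For the primary endpoint, SAP 8.5.1 states: "Annualized MCE event rate will be calculated for the entire study period 1 and by 18-month interval". SAP 8.5.2 treats the secondary event and duration rates in the same way. For CL201 rollovers, SAP 8.5.5.1 calculates the same intervals within study period 1 and adds that "annualized event/duration rates will be plotted as box plots over time to show the time trend".

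On who is counted, SAP 6.1 says: "The full analysis set (FAS) will consist of all subjects enrolled and had at least one post-baseline efficacy assessment". For the denominator over study period 1, SAP 5.11 says that "the number of days is calculated from study day 1 till the data cutoff date or the early termination/study completion visit date", the latter for subjects who have left or finished. SAP 7.2.4 adds only that a missing exit date is replaced by the date of the last assessment.

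On leaving, protocol 7.3.3.1 covers a major LC-FAOD event that changes in nature or becomes more frequent relative to the subject's medical history. In that case "the Investigator should determine whether the subject should be discontinued from the study". Protocol 7.5.2.3 has a similar trigger: "the event should be reported as an adverse event (AE) and the Investigator should evaluate whether the subject should be discontinued from the study". Section 7.3.3.1 also provides that the "subject visit schedule may need to be modified or assessments withheld to allow the subject to continue as deemed appropriate by the Investigator".

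**The concern.** The SAP does not restrict the intervals to a common set of subjects, set a minimum observed time within an interval, or address discontinuation that depends on the endpoint. The natural reading is that interval k contains everyone observed for any part of it. That is an inference from SAP 5.11 and 6.1, because the SAP never states it.

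The protocol makes worsening of the primary endpoint an occasion to consider ending participation. If some subjects leave for that reason, later intervals hold a different mix of people from earlier ones. A stable or falling series could then be read as sustained benefit when part of it is a change in composition. A real loss of effect could be masked in the same way. The sensitivity analyses in SAP 8.5.4.2 and 8.5.5.2 (negative binomial model, outlier removal, alternative MCE definitions) concern the pre/post comparisons and do not touch the interval series.

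**Working it through.** **1. The plan's own arithmetic.** With the SAP 5.5 conversion, 18 × 30.4375 = 547.9 days, which agrees with the 548 days in SAP 5.10.3. Follow-up of up to 84 months gives 84/18 = 4.67, that is, four full intervals and a 12-month remainder. The documents state no expected MCE rate, dropout rate or trend, so there is no figure to reproduce. Every rate below is an assumption. In every case each subject's true rate is constant, so a correct trend is flat.

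**2. Two-group mixture.** Half the subjects have 0.5 MCEs per year and half have 3.0. The groups leave at d_L and d_H per interval. The mean in interval k is

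[0.5·(1−d_L)^(k−1)·0.5 + 0.5·(1−d_H)^(k−1)·3.0] / [0.5·(1−d_L)^(k−1) + 0.5·(1−d_H)^(k−1)].

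At k = 5 with d_L = 5% and d_H = 20%, the weights are 0.5 × 0.95⁴ = 0.407 and 0.5 × 0.80⁴ = 0.205. The mean is (0.407 × 0.5 + 0.205 × 3.0)/0.612 = 1.34, against 1.75 in interval 1.

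| d_L / d_H | Interval 1 | Interval 5 | Change |
|---|---|---|---|
| 10% / 10% | 1.75 | 1.75 | 0% |
| 5% / 10% | 1.75 | 1.62 | −8% |
| 5% / 20% | 1.75 | 1.34 | −24% |
| 10% / 30% | 1.75 | 1.17 | −33% |
| 10% / 40% | 1.75 | 0.91 | −48% |

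**3. Exit triggered by the subject's own history, closer to the protocol's wording.** This is a simulation of 200 × 150 subjects with gamma-distributed rates (mean 1.5 per year, shape 0.7) and Poisson events. After each event, if the count in the last 18 months exceeds the subject's own 18-month history, the subject leaves one month later with probability p. Rates follow SAP 5.11: events / (days observed/365.25). The mean of subject rates by interval was:

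| Leaving | 0–18 m | 18–36 m | 36–54 m | 54–72 m | 72–84 m | First to last | Entering last |
|---|---|---|---|---|---|---|---|
| None | 1.51 | 1.51 | 1.50 | 1.51 | 1.51 | 0% | 100% |
| Random, 10%/yr | 1.49 | 1.50 | 1.51 | 1.51 | 1.51 | about 0% | 55% |
| p = 0.05 | 1.52 | 1.57 | 1.45 | 1.36 | 1.27 | −16% | 83% |
| p = 0.1 | 1.55 | 1.59 | 1.42 | 1.25 | 1.14 | −26% | 73% |
| p = 0.2 | 1.62 | 1.68 | 1.37 | 1.19 | 1.06 | −35% | 60% |
| p = 0.4 | 1.73 | 1.74 | 1.36 | 1.15 | 0.98 | −43% | 47% |

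The series is not monotone. A subject who leaves soon after an event contributes a short interval with a high rate: one event in two months is 1/(2/12) = 6 per year. This lifts interval 2. Dividing total events by total person-time removes the bump but not the fall: at p = 0.1 the values are 1.48, 1.34, 1.21, 1.10 and 1.04, a drop of 1 − 1.04/1.48 = 30%.

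**4. The same subjects throughout.** Among those observed through all five intervals in the same simulation, the first and last means were 1.13 and 1.14 (p = 0.05), 0.94 and 0.96 (0.1), 0.81 and 0.82 (0.2), and 0.68 and 0.70 (0.4). The spread across intervals was never more than 0.06. The trend is repaired. The level is not: it lies below the true 1.5 because completers are a selected group.

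**The case against.** Several points against the concern have force.

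- **The protocol prompts; it does not remove.** The trigger is relative to the subject's own history, the instruction is to consider discontinuation, and continuation with adapted visits is expressly allowed. A subject with a stable high rate meets the trigger only by chance. A reader might infer that frequent-event subjects are selectively taken out; the documents do not say so.
- **The SAP gives some within-subject visibility.** SAP 8.5.4.1 compares 18 months before and after treatment start within naïve subjects. SAP 8.4.1 plans individual profiles with MCEs over time. SAP 8.5.5.1 plans patient-level MCE plots marking early discontinuation. SAP 8.2 tabulates discontinuation reasons, and SAP 8.1 reports n. It would be wrong to say that nothing compares like with like. Still, none of these sets the same subjects' early and late intervals side by side or shows whether leavers had higher rates.
- **Staggered entry adds little to the only display that the SAP calls a trend.** The Amendment 6 summary describes continuing enrolment from investigator-sponsored trials and of naïve subjects, and SAP 8.5 presents results by cohort, so the rollover plot is unaffected. A reader might also infer that anyone entering after Amendment 6 (1 October 2019) contributes to interval 1 only. The 447 days (14.7 months) behind that run to the SAP's date of 21 December 2020, and no data cutoff is stated.
- **The use is descriptive.** Maintenance of efficacy is a design aim, not a listed objective, and the whole-period rate is reported as well.
- **Medians are less sensitive.** In the simulation the median was 0.67 in each of the first four intervals for p up to 0.2, so a box plot's centre line may show little.

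These points limit the size and reach of the concern. They do not settle who is in each interval.

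**Conclusion.** The point holds conditionally. As written, the interval series mixes any change in subjects' rates with change in who is observed, and the protocol supplies a plausible link between leaving and the endpoint. If leaving is related to MCEs, the means can fall with no subject changing. If it is unrelated, and the entry mix is constant, there is no fall. The 8% to 48% range rests wholly on assumed rates and exit probabilities; the actual size cannot be derived from the documents.

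A reader might go further and conclude that any observed decline is an artefact, or that durability cannot be assessed at all. Neither follows: the documents do not show how often the prompt leads to discontinuation. The whole-period rate has no interval-composition problem, although event-triggered exit pushed its mean up in the simulation (1.60 to 1.92 against a true 1.5). Because the display is descriptive and no test depends on it, this is an improvement that should be made rather than a flaw in the primary analysis.

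**What to change.** In SAP 8.5.1 and 8.5.5.1:

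1. Keep the all-available display, by cohort. State who enters each interval, and give n and person-time per interval.
2. Beside it, for each later interval k, show the interval-1 rate, the interval-k rate and the within-subject difference for subjects observed through the end of interval k. This excludes short partial intervals. Define the final interval as months 72 to 84.
3. Among subjects who completed interval 1, tabulate the interval-1 rate (and the pre-UX007 rate where collected) for those who later discontinued and those who continued, by discontinuation reason. Follow-up ended by data cutoff or commercial availability should not count as discontinuation; protocol 7.1 already records the latter as completion.
4. State the limits: the same-subject display corrects the trend for changing composition but not the level, cannot show loss of effect in those who left, and becomes small in late intervals.

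A table of leavers' rates in their last six months on study should not be used for step 3. Anyone who leaves soon after an event has at least one event in that window, so a rate of at least 1/0.5 = 2 per year, even if the true rate is low and constant.

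The cost is SAP wording and two tables from data already collected. No change to the discontinuation rule is proposed.
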